7.1.2.2.3 Repeatable Battery for the Assessment of Neuropsychological Status (RBANS)

The Repeatable Battery for the Assessment of Neuropsychological Status¹⁵ (RBANS) is a commonly used 25-minute, standardized neurocognitive battery assessing functioning across multiple cognitive domains. It is designed to be administered repeatably, with several equivalent alternate forms available. The RBANS measures a total of five neurocognitive domains using twelve subtests: immediate memory (List Learning and Story Memory), visuospatial/constructional (Figure Copy and Line Orientation), language (Picture naming and Semantic Fluency), attention (Digit Span and Coding), and delayed memory (List Recall, List Recognition, Story Memory, and Figure Recall). The RBANS has been shown to be effective at both detecting and characterizing forms of dementia. The Delayed Memory domain has been shown to be particularly sensitive to discriminating MCI due to Alzheimer's disease from controls, and also is predictive of cerebral amyloid burden¹⁵. The RBANS will be administered at Baseline, Crossover, and End of Study using alternate forms. The RBANS will be administered virtually via Zoom videoconference. The coding subtest response form will be mailed or given to subjects before their scheduled visits along with a prepaid envelope for the form to be returned.

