9. STATISTICAL ANALYSIS

9.1 Biostatistical analysis

This is a crossover randomized controlled trial with the goal of determining the effects of a potential cognitionenhancing dietary supplement for older adults with SCD and MCI. The primary analysis will be based on an intention to treat approach and will include all subjects randomized at the onset of the trial to either NR then placebo or placebo then NR as described below.

In this study, the participants will pass through intervention blocks with administration of both NR and PBO for eight weeks administered in random order. The primary cognitive outcome measure will be the Total Scale score of the RBANS which will be administered at Baseline (Day 28), Crossover (Day 84), and End of Study (Day 140). The RBANS is a robust 25-minute, standardized neurocognitive battery with multiple alternate versions whose 12 subtests yield five Index scores, one for each cognitive domain, and the Total Scale score.

A Crossover, Randomized Block Sequence, Double-Blind, Placebo-Controlled Trial for Nicotinamide Riboside in Subjective Cognitive Decline and Mild Cognitive Impairment in Aging

Version:4.4

Normative data have been published for cognitively normal older adults, as well as for MCI and AD populations. For example, in a study of MCI, the mean Total Score Index was reported to be 92.4 with a standard deviation of 9.1⁴³. Based on test-retest reliability, a minimal detectable change in community-dwelling older adults (including normal, MCI and mild dementia) for the Total Score is 5⁴³. A "minimum clinically important difference" in MCI was reported to be 8 points⁴⁴.

The basic data of a crossover trial are the measurements obtained in 2 or more different intervention conditions occurring over time. The principal goal is to compare outcomes for each condition within a randomized block structure while accommodating repetition *within* subjects and possible effects of carryover or disease progression.

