Assessment of normality of data distribution will be completed prior to inclusion in any analysis. If the distribution of the outcome variables (e.g., RBANS Total Score, etc) are not normal, appropriate transformations (e.g., logarithm, square-root, Box-Cox transformation, etc) will be applied. Data analysis at the individual and group levels for the primary outcome will begin with visual inspection of RBANS Total Scores at each assessment for differences from baseline for each measurement and differences between intervention conditions. Ignoring potential for carryover, a simple matched pair t-test will be performed using data from each condition. Should carryover effects or other time trends be suspected, we can use a regression model adjusting for sequence.

Mixed-effects models will be used to compare the scores at the end of each study period (Days 28, 84, and 140) between NR and PBO incorporating variance within and between participants. This within-patient level will accommodate variation resulting from the intervention crossovers as well as time effects modeled in various forms (e.g., linear and non-linear trends, carryover effects). Each within-subject regression coefficient will be treated as a random effect that can vary based on these between participant factors. The primary analysis will calculate the average intervention effect (i.e., will model the mean of the individual intervention effects as a constant). Secondary analyses will model the mean as a function of factors that vary among patients such as age and sex. These terms describe the main effects of these factors, their interactions with the intervention, and their interaction with time. The analysis will be completed using SAS PROC MIXED through a restricted maximum likelihood analysis with a mixed model with fixed effects for sequence and treatment. Appropriate covariance structure will be investigated using Akaike's information criterion (AIC).

The full multilevel model will estimate both average effects across the population of participants, as well as effects for individuals informed by the results on other participants. The predicted effects for an individual participant are weighted averages of his or her data and the averages from others. This model incorporates correlations among the measurements within an individual and enables comparison of the individual's predicted intervention effect using the multilevel model with that from using only that individual's data.

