When conducting study analyses we can also calculate 95% confidence intervals for the difference in response for active treatment versus placebo treatment for descriptive purposes. Similar analyses will be applied to all

A Crossover, Randomized Block Sequence, Double-Blind, Placebo-Controlled Trial for Nicotinamide Riboside in Subjective Cognitive Decline and Mild Cognitive Impairment in Aging

Version:4.4

outcomes. All outcomes in this pilot study are considered exploratory and no claims are attached to them, thus multiple comparison correction is not applied. Therefore P value <0.05 will be considered significant.

Carryover is always a potential confound in crossover studies. While the pharmacokinetic half-life of NR is short (2.7 hours), its pharmacodynamic effects may be long-lived and we cannot exclude carryover and practice effects affecting measures in successive assessments if NR precedes PBO. We do not expect carryover pharmacological effects from PBO, but assessment practice effects might differentially affect measurements made in an NR intervention period that follows PBO. This may be difficult to gauge with our primary RBANS outcome measure taken only once at the beginning/end of each intervention period. However, we will have other resources with which to evaluate this using our exploratory outcomes, especially the daily cognition measures. We will investigate various adjustments for carryover, such as discarding the first measurements in an intervention period on outcomes measured daily, to determine whether results are sensitive to carryover. These adjustments can allow for potential differential carryover by intervention regimen.

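### The planned matched-pair t-test on RBANS has no period term, so any Day 84 to Day 140 shift in scores costs precision, and the mixed model as listed does not clearly remove it

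*Combined protocol and SAP*

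**What the plan says.** The RBANS Total Scale score is "administered at Baseline (Day 28), Crossover (Day 84), and End of Study (Day 140"), so the two randomized periods end at Days 84 and 140. Section 9.1 then describes these analyses of it:

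- A paired test without any condition: "Ignoring potential for carryover, a simple matched pair t-test will be performed using data from each condition".
- An optional adjustment: "Should carryover effects or other time trends be suspected, we can use a regression model adjusting for sequence". No criterion for suspicion is given.
- Mixed-effects models, also without condition. They mention "time effects modeled in various forms (e.g., linear and non-linear trends, carryover effects"), but the PROC MIXED statement specifies a "mixed model with fixed effects for sequence and treatment". Period (visit) is not in that list.

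The section does not rank the t-test against the mixed model for RBANS. On practice, it says that "assessment practice effects might differentially affect measurements made in an NR intervention period that follows PBO", and it concedes that such effects may be hard to judge on an outcome measured once per period. Section 7.1.2.2.3 adds a design safeguard: "The RBANS will be administered at Baseline, Crossover, and End of Study using alternate forms".

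**The concern.** In a two-period crossover, every subject's NR minus PBO difference contains the period difference. Its sign is positive if NR came second and negative if NR came first. A matched-pair t-test pools the two groups and treats that systematic split as random error. The interval is then wider than the data require, and small effects are easier to miss. If the two sequences contribute unequal numbers, part of the shift also enters the estimate.

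RBANS is given three times, so a shift from practice or from non-equivalent forms is plausible. The plan acknowledges the possibility but makes adjustment discretionary. With about 40 subjects, the precision gained from within-subject comparison is the main reason to use a crossover.

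**Working it through.** **Inputs from the documents.** 40 subjects (3.1; 4.2 expects about 40 completers); two counter-balanced sequences (5.3), taken as 20:20; RBANS Total SD 9.1 (9.1); significance at 0.05 (9.1), taken as two-sided.

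**Assumed, because the documents give no value.** Test-retest correlation r from 0.80 to 0.95; shift p (Day 140 minus Day 84, same treatment) from 0 to 4 points; an illustrative effect of 1.5 points. The test is taken to compare end-of-period scores. If it used change from each period's own start, p would be the difference between the two practice gains. The plan gives no power or sample-size figure to reproduce.

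**Algebra.** Let d be a subject's NR minus PBO score and τ the true effect.

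- PBO then NR (n1 subjects): E(d) = τ + p
- NR then PBO (n2 subjects): E(d) = τ − p
- Paired t-test: estimate = mean of all d, with bias p(n1 − n2)/N. At 20:20 the expected sample variance is sd² + (40/39)p².
- Period-adjusted: average of the two sequence means of d, with pooled within-sequence variance sd² and N − 2 degrees of freedom. Bias is zero for any split.

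Here sd = 9.1 × √(2(1 − r)), which gives 5.76 at r = 0.80, 4.07 at 0.90 and 2.88 at 0.95.

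**Standard-error ratio at 20:20**, √(1 + (40/39)p²/sd²):

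| r | p = 0 | p = 2 | p = 3 | p = 4 |
|---|---|---|---|---|
| 0.80 | 1.00 | 1.06 | 1.13 | 1.22 |
| 0.90 | 1.00 | 1.12 | 1.25 | 1.41 |
| 0.95 | 1.00 | 1.22 | 1.45 | 1.73 |

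Worked case, r = 0.90 and p = 3: (40/39) × 9 = 9.23; sd² = 16.56; √(1 + 9.23/16.56) = 1.25. The SE is 4.07/√40 = 0.64 with adjustment and 0.64 × 1.25 = 0.80 without.

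In the extreme corner the squared ratio is 2.98, and 40/2.98 = 13.4, so the paired test performs like an adjusted analysis of about 13 subjects.

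**Operating characteristics** (simulation, 40,000 trials per scenario, 20:20):

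- r = 0.90, p = 3: type I error about 1.5%, coverage about 98.5%, power for 1.5 points about 43% against 62% adjusted.
- r = 0.90, p = 4: power for 1.5 points about 31% against 62 to 63%.
- A 5-point effect: paired-test power at least 99.8% at every combination in the table.

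**Unequal sequences.** At 22:18 and p = 3, bias = 3 × (22 − 18)/40 = 0.30 points. The sign reverses if the NR-first group is larger. The adjusted bias is zero.

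**Does the listed mixed model cure it?** On raw scores, a sequence term describes differences between subjects' averages, whereas the period shift lies within subjects. REML fits to simulated Day 84 and Day 140 scores (true effect 2.5, p = 3, sd 5.76) gave SE 1.03 with sequence and treatment only, against 0.91 with period added, at 20:20. At 24:16 the estimates were 3.11 without period and 2.49 with it. A sequence term in a regression on within-subject differences would remove the shift, but the plan does not say that its optional regression takes that form.

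**The case against.** The strongest reply is that the t-test is only a preliminary step. The phrase about what the primary analysis will calculate stands in the mixed-model paragraph, and that model is fitted in any case. This largely stands. A reader might infer that the paired t-test is the declared primary test; the documents never label it so. What remains is that the hierarchy is not stated and that the listed mixed-model terms also omit period.

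Other stronger readings also go beyond the text:

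- **That the adjustment is decided after seeing treatment differences.** Section 9.1 describes a visual inspection, but no sentence ties suspicion of a trend to it. The gap is the missing criterion.
- **That the all-randomized promise is broken.** The commitment that the analysis "will include all subjects randomized at the onset of the trial" attaches to the primary analysis, and a REML mixed model keeps subjects with one score.
- **That the plan predicts practice effects.** It says only that they cannot be ruled out. Alternate forms may reduce them, and the relevant shift is between the second and third administrations. It could be zero.
- **That false positives are the risk.** At 20:20 the test is unbiased and conservative.
- **That the 12-subject MRI and lumbar-puncture sub-studies inherit a bias.** Chance splits between sequences average to zero bias. Simulated type I error over such splits stayed at about 3% to 5%, and nothing in the documents suggests a practice shift in imaging or CSF measures.

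It is also fair to say that section 9.1 calls the trial a pilot with exploratory outcomes, and that its only RBANS benchmarks, 5 and 8 points, lie where little power is lost.

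**Conclusion.** The concern holds as an avoidable loss of precision of unknown size, of moderate importance. The variance inflation follows from algebra; its size depends on an assumed shift and correlation. Over the ranges used, the paired test's standard error is 0% to 73% too large, with 25% at r = 0.90 and shift 3. If the shift is zero, nothing is lost. For effects of 5 points or more, power is hardly affected. Bias arises only if the analysed sequences are unequal, and it is small for mild imbalance (0.3 points at 22:18 and shift 3).

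The case for acting is the asymmetry: adjustment costs almost nothing if there is no shift, and it recovers material power for small effects if there is one.

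**What to change.** In section 9.1:

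1. Name one decisive RBANS analysis: the REML mixed model with treatment, period (visit) and sequence as fixed effects and subject as random, always applied.
2. Keep the matched-pair t-test as descriptive only, or replace it with a two-sample comparison between sequences of half the Day 84 minus Day 140 difference.
3. Delete the condition that time trends must first be suspected.

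The same amendment settles the missing period term in the PROC MIXED list, so the two should be handled together. The cost is SAP wording and one degree of freedom; no change to visits, data collection or sample size is needed.

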3. SPECIFIC AIMS

3.1 Overall Study Design and Plan

This is a single-site single crossover, double-blind placebo (PBO)-controlled randomized sequence block trial of nicotinamide riboside (NR, TruNiagen®, Chromadex) vs. PBO in 40 volunteers with SCD or MCI. All volunteers will receive a four-week PBO-lead in and acclimatization followed by two 8-week "blocks". Each block consists of either NR or PBO for an 8-week period in random assignment order. Outcomes will consist of standardized cognitive, neuropsychiatric, functional and biomarker assessments as well as daily cognitive, mood, sleep, and activity monitoring with computer-based brain games and wearable actigraphy. Due to the COVID-19 pandemic, some of the study visits will be completed fully or partially via Zoom videoconference to minimize the amount of contact between study staff and research subjects.

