6.1.6 Early Termination Visit

If the subject withdraws from the study after the Baseline visit and before completion of all study visits, they will be invited to participate in an Early Termination Visit within 7 days of stopping treatment.

The following procedures will be performed virtually via Zoom videoconferencing no more than 4 days before the in-person office visit:

- Administer cognitive assessments
- Administer functional and mood assessments
- Assess technology and study supplement compliance.
- Review and document concomitant medications, supplements, and therapies
- Assess and document AEs and changes to medical history

The following procedures will be performed at the in-person office visit:

- Measure Vital Signs
- Blood draw for safety labs and biomarker analysis
- Assess study supplement compliance

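### Section 9.1 plans two NR-versus-placebo analyses of RBANS that can use different subjects, does not rank them, and lists no period effect in the model that keeps one-block subjects

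*Combined protocol and SAP*

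**What the plan says.** All of this is in section 9.1 of the combined protocol and SAP unless noted.

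- **Population.** "The primary analysis will be based on an intention to treat approach and will include all subjects randomized at the onset of the trial".
- **Paired test.** "Ignoring potential for carryover, a simple matched pair t-test will be performed using data from each condition". No population is given for it, and it is called neither primary nor supportive. The fallback reads "Should carryover effects or other time trends be suspected, we can use a regression model adjusting for sequence". Its trigger is carryover or a time trend, not missing data.
- **Mixed model.** "Mixed-effects models will be used to compare the scores at the end of each study period (Days 28, 84, and 140"). In the same paragraph: "The primary analysis will calculate the average intervention effect". The fitting line specifies a "restricted maximum likelihood analysis with a mixed model with fixed effects for sequence and treatment", run in SAS PROC MIXED. The paragraph also says that time effects may be modelled in various forms, but it names none as a term of the primary fit.
- **Decision rule.** P below 0.05 counts as significant. All outcomes are described as exploratory, with no correction for multiplicity.
- **Early leavers.** Section 6.1.6 offers an Early Termination visit with cognitive testing "If the subject withdraws from the study after the Baseline visit and before completion of all study visits".

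Section 9.1 has no rule for missing RBANS scores.

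**The concern.** A paired test needs a score under NR and a score under placebo from the same person. Someone who leaves during block 1 or at crossover has at most one of these and drops out of the test, even with valid Day 28 and Day 84 scores. Such subjects are foreseeable: section 5.4 lists withdrawal for adverse events and for poor dosing compliance, and section 6.1.8 covers missed visits. The t-test therefore cannot meet the statement that all randomised subjects are included. The mixed model can come close.

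Two things are at stake. First, with no ranking, the choice between two results on different subjects can be made after the data are seen. Second, if leaving depends on how block 1 went, the remaining pairs are selected on the primary outcome. Choosing the mixed model does not settle this by itself, because the result depends on how Day 28 and period enter it.

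**Working it through.** The plan gives no power, dropout rate or within-subject correlation, so there is no planned figure to reproduce.

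**Inputs from the documents.** RBANS Total SD 9.1 (9.1); size "in 40 volunteers with SCD or MCI" (3.1). Section 4.2 instead expects about 40 completers, so the number randomised could be larger.

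**Assumed.** 20 subjects per sequence; equal correlation r between visits of 0.70 to 0.85; practice gain g of 0 or 3 points per visit; no true NR effect; leavers are the k subjects of one sequence with the worst Day 28 to Day 84 change, and they have no second-block score.

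**Step 1: who is used.** If 5, 10, 15 or 20% of 40 lack a second-block score, the t-test uses 38, 36, 34 or 32 pairs. A likelihood model uses all 40, provided each has some RBANS score.

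**Step 2: selection in the depleted sequence.** The change has SD s = 9.1 × √(2(1 − r)). The slope of Day 84 on the change is (1 − r)/(2(1 − r)) = 0.5, and that of Day 140 is 0. The retained subjects' Day 84 mean is therefore too high by δ = 0.5 × s × m. Here m is their mean standardised change, from the expected lowest normal order statistics of 20:

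- k = 2: m = (1.867 + 1.408)/18 = 0.182
- k = 4: m = (1.867 + 1.408 + 1.131 + 0.921)/16 = 0.333

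**Step 3: effect on the t-test.** Suppose the leavers are NR-first, leaving n₁ NR-first and n₂ = 20 placebo-first pairs. The mean NR-minus-placebo difference is [n₁(δ − g) + n₂g]/(n₁ + n₂).

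Example, r = 0.80, k = 4: s = 5.76 and δ = 0.5 × 5.76 × 0.333 = 0.96. With g = 3 the bias is (16 × 0.96 + 4 × 3)/36 = 0.76. With g = 0 it is 15.36/36 = 0.43.

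| r | s | 2 leave, g = 0 | 2 leave, g = 3 | 4 leave, g = 0 | 4 leave, g = 3 |
|---|---|---|---|---|---|
| 0.70 | 7.05 | 0.30 | 0.46 | 0.52 | 0.85 |
| 0.80 | 5.76 | 0.25 | 0.41 | 0.43 | 0.76 |
| 0.85 | 4.98 | 0.21 | 0.37 | 0.37 | 0.70 |

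If the leavers are placebo-first, every entry changes sign. If both sequences lose the same number, the terms cancel. For scale, the standard error with 36 pairs at r = 0.80 is 5.76/√36 = 0.96, so the worst case in that row is about 0.8 of a standard error.

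Simulation (1,000 trials per setting, r = 0.80, g = 3) agrees. With four NR-first leavers the t-test bias was 0.75, a period-adjusted completer contrast gave 0.47, and generalised least squares on all scores with period effects gave −0.01. With two leavers the figures were 0.37, 0.22 and −0.04.

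**Step 4: does the listed mixed model avoid this?** That depends on its form.

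- *Days 84 and 140 only, sequence and treatment:* it ignores the Day 28 score that helped drive dropout, and in simulation it kept dropout bias.
- *Days 28, 84 and 140, sequence and treatment, Day 28 counted as placebo:* practice leaks into the treatment effect even with complete data. Centred treatment codes are (−1/3, 2/3, −1/3) for NR-first and (−1/3, −1/3, 2/3) for placebo-first. Against visit means 0, g, 2g the cross-products are 0 and g, and each sum of squares is 2/3. Bias = (0 + g)/(2/3 + 2/3) = 0.75g, or 2.25 points at the assumed g = 3 and zero at g = 0.
- *Day 28 as a pre-treatment response, with treatment and period effects, all scores:* within about 0.1 point of zero in every setting run.

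**The case against.** The strongest reply is that 9.1 already makes the mixed model the primary intention-to-treat analysis. The population sentence refers to what is described below it, and the words primary analysis next appear in the mixed-model paragraph. The t-test belongs to an opening descriptive step and is qualified as ignoring carryover. This largely stands. A reader might infer that a completer result would be reported as intention to treat; the documents do not support that, because no sentence gives the t-test that label. Nor does 9.1 state two conflicting populations: the restriction follows from how a paired test works. What remains is that the ranking has to be inferred.

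A reader might also infer that the t-test would flatter NR. The direction is not established. In the crossover trial cited in section 2.1.5, 2 of 30 subjects dropped out and both were in the placebo period. Section 10.1.1 says no reported event led to stopping NR. In a further simulation with a true effect of 5 and the same decline-driven dropout rule in both sequences, the t-test understated NR (4.83 at r = 0.80, 4.64 at r = 0.70). A mixed model including Day 28, simulated without practice gain, gave 5.03 and 4.93.

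Three further points have weight. Early Termination testing can supply a second-condition score for someone who leaves in block 2, and section 8.4.1 implies that a subject may stop product and stay in the study, so not every early stop costs a pair. The bias is small beside the 5-point detectable change and 8-point important difference that 9.1 cites, and the dropout rule used here is deliberately severe. Finally, 9.1 allows time effects, so the two listed fixed effects may not be the whole model; but a choice left open is not a specification.

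**Conclusion.** The point holds in limited form. Section 9.1 commits to two RBANS comparisons with different usable subjects, does not rank them explicitly and has no missing-data rule. Under dropout that differs by sequence and depends on observed change, the t-test is biased by roughly 0.2 to 0.5 point with two one-sided leavers and 0.4 to 0.9 with four. The bias can go either way and is about zero when losses are equal. These sizes rest on the assumed dropout, correlation and practice gain; only the SD and the number 40 come from the documents.

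A ranking sentence alone is not enough. The sequence-and-treatment model can keep the dropout bias or, with Day 28 counted as placebo, absorb 0.75 of any per-visit practice gain. Severity is minor to moderate: this is a pilot whose outcomes are called exploratory, but RBANS is its primary outcome and will be read at P below 0.05.

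**What to change.** In 9.1:

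1. State that the PROC MIXED model is the single primary intention-to-treat analysis, fitted to every randomised subject with any RBANS score.
2. Specify Day 28 as a pre-treatment response, with treatment and period effects.
3. Label the matched-pair t-test a supportive analysis of subjects with an RBANS score in both blocks, and say whether Early Termination scores count.
4. Report the number contributing to each analysis by sequence.
5. State the missing-at-random assumption.

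The cost is wording: no new data and no new software. There are three downsides. The result relies on missing at random. Subjects lost in the lead-in enter neither analysis, because the section 6.1 schedule randomises at Day 0 and the first RBANS is at Day 28. Period terms also give up some nominal precision: at r = 0.70 with 20% loss the standard error is 1.20, against 1.03 if Day 28 is counted as placebo with no period term. That smaller figure is valid only if there is no practice or time trend.

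### Adjusting for sequence does not remove carryover from the RBANS effect of NR, and no visit or carryover term is fixed for RBANS

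*Combined protocol and SAP*

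**What the plan says.** The design (section 3.1) gives everyone a placebo lead-in ("All volunteers will receive a four-week PBO-lead in and acclimatization") and then two consecutive blocks: "Each block consists of either NR or PBO for an 8-week period in random assignment order". No washout between the blocks is described. RBANS Total Scale, the primary outcome, is measured at Days 28, 84 and 140.

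Section 9.1 begins with a paired t-test that ignores carryover, and continues: "Should carryover effects or other time trends be suspected, we can use a regression model adjusting for sequence". It then describes mixed models comparing NR with placebo on the scores at Days 28, 84 and 140. These are to allow for "time effects modeled in various forms (e.g., linear and non-linear trends, carryover effects", but the PROC MIXED analysis itself is specified as "a mixed model with fixed effects for sequence and treatment".

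The same section says of NR that "its pharmacodynamic effects may be long-lived and we cannot exclude carryover and practice effects" affecting later assessments. On assessing this with RBANS it says: "This may be difficult to gauge with our primary RBANS outcome measure taken only once at the beginning/end of each intervention period". It promises to investigate various adjustments. The one it describes, dropping early measurements in a period, applies to outcomes measured daily.

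**The concern.** Sequence is a between-subject factor and the NR minus placebo contrast is within-subject. A sequence term in a model for the scores therefore absorbs a difference in mean level between the two groups and leaves the treatment contrast essentially where it was. Regressing each subject's paired difference on sequence is a sound way to remove a period effect, so the plan's sentence is right about other time trends. It is not a remedy for carryover.

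A second problem comes from Day 28, which is always placebo and always first. In a model with no visit term it acts as one more placebo score, so part of any practice gain is credited to NR.

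The two biases pull in opposite directions, so a reader cannot tell whether the reported effect is too small or too large. The plan itself says that neither carryover nor practice can be excluded, yet it commits to no RBANS estimate that is free of carryover.

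**Working it through.** The plan gives no power or bias figure to reproduce, so the check is a derivation.

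**Inputs from the documents:** 40 participants in two counter-balanced sequences (sections 3.1, 5.3); RBANS at Days 28, 84 and 140; SD 9.1 in MCI and a minimum clinically important difference of 8 points (section 9.1).

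**Assumptions:** 20 per sequence; within-subject correlation ρ = 0.7, 0.8 or 0.9; compound symmetry unless stated; λ = 0, 2, 4 or 8 points; linear practice gain g = 0 or 2 points per visit. Here τ is the true NR effect, λ is the NR effect still present at Day 140 in the NR-first sequence, and v28, v84, v140 are visit effects.

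**1. Paired or period-adjusted estimate (Days 84 and 140)**

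- NR-first: Day 84 − Day 140 = τ + (v84 − v140) − λ
- PBO-first: Day 140 − Day 84 = τ + (v140 − v84)
- Average: **τ − λ/2**. The visit effects cancel and the carryover does not.
- SE = √[9.1²(1 − ρ)/20] = 1.11 / 0.91 / 0.64 for ρ = 0.7 / 0.8 / 0.9

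**2. Listed model (sequence + treatment, three visits)**

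Under compound symmetry the treatment estimate is each subject's NR score minus the mean of that subject's two placebo scores, averaged over sequences.

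- NR-first: τ + v84 − (v28 + v140)/2 − λ/2
- PBO-first: τ + v140 − (v28 + v84)/2
- Average: τ − λ/4 + (v84 + v140)/4 − v28/2. With visit effects 0, g, 2g this is **τ − λ/4 + 0.75g**.
- SE = √[9.1²(1 − ρ) × 1.5/40] = 0.97 / 0.79 / 0.56

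Generalised least squares gives these same coefficients with and without the sequence term.

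| λ (assumed) | Paired or period-adjusted bias | Listed model, g = 0 | Listed model, g = 2 |
|---|---|---|---|
| 0 | 0 | 0 | +1.5 |
| 2 | −1 | −0.5 | +1.0 |
| 4 | −2 | −1 | +0.5 |
| 8 | −4 | −2 | −0.5 |

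For τ = 8 and λ = 4 the expected readings are 8 − 2 = 6; 8 − 1 = 7; and 8 − 1 + 1.5 = 8.5.

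With τ = 0, λ = 0 and g = 2, simulation of the equivalent within-subject contrast (20,000 trials, ρ = 0.8) gave a mean of +1.5 points and p < 0.05 in about 42% of trials.

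**3. AR(1) covariance, which the AIC step could select**

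For ρ = 0.7 / 0.8 / 0.9 the listed model's coefficients are −0.315 / −0.321 / −0.328 on λ and +0.426 / +0.393 / +0.362 on g. Dropping sequence gives −0.330 / −0.332 / −0.333 on λ, so the sequence term moves the carryover coefficient by at most 0.015.

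**4. Adding categorical visit**

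The practice coefficient becomes 0. The carryover coefficient becomes −0.5 under compound symmetry (−0.42 to −0.41 under AR(1)). The SE at ρ = 0.8 under compound symmetry goes from 0.79 to 0.91.

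**5. Day 84 between sequences, adjusted for Day 28**

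Both visits precede any NR-to-placebo switch, so bias from λ is 0, and practice is common to the two groups.

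- SE = √[9.1²(1 − ρ²) × 2/20] = 2.06 / 1.73 / 1.25
- A mixed model with treatment, visit and an NR-carryover indicator at Day 140, without sequence, gives the same estimate and SE. Keeping sequence in that model raises the SE to 2.23 / 1.82 / 1.29.

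**6. How well λ itself can be estimated**

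The first-block estimate minus the period-adjusted estimate equals λ̂/2. At ρ = 0.8 its SE is √(1.727² − 0.910²) = 1.47, so SE(λ̂) = 2.9. For ρ = 0.7 and 0.9 it is 3.5 and 2.2. Power to detect λ = 4 (two-sided 0.05, normal approximation) is about 21% / 28% / 46%.

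**The case against.** The algebra is hard to dispute. The case against rests on how the plan is read and how much the point weighs.

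- **Time and carryover are mentioned.** The sequence and treatment terms are not said to be the complete list. With the linear trend that section 9.1 mentions, linear practice bias goes to 0. This is fair, and the defect is that nothing is fixed, not that time is ignored. But a linear trend alone leaves a carryover coefficient of −0.54 (about −0.47 under AR(1)) and still credits NR with 0.15 to 0.18 point per point of a one-step practice gain after Day 28.
- **Day 28 may be meant as a baseline.** Other sections call it that, and the three-visit figures would not apply if it were modelled so. However, section 9.1 lists Day 28 among the end-of-period scores compared between NR and placebo. The −λ/2 result does not depend on this.
- **λ and g are assumed.** Carryover would have to last eight weeks on placebo, the NR half-life is 2.7 hours, and RBANS uses alternate forms (section 7.1.2.2.3). All of this argues for small values, and λ = 0 is in the table. The plan nonetheless says both effects remain possible.
- **The limitation is disclosed and the pilot is exploratory.** This lowers the stakes. The plan still applies p < 0.05, and disclosure does not supply an estimate.
- **Adding visit alone increases the carryover coefficient.** This is true, and it is why the first-block analysis has to accompany it.

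**Conclusion.** The concern holds. Sequence adjustment does not correct the RBANS treatment effect for carryover, and the plan fixes neither a visit term nor a carryover term for RBANS. The carryover bias is −λ/2 for the paired or period-adjusted estimate. For the listed three-visit model it is −λ/4 under compound symmetry or about −0.32λ under AR(1). That model also picks up +0.75 (compound symmetry) or +0.36 to +0.43 (AR(1)) per point of linear practice gain per visit.

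The direction of the carryover result does not depend on the assumed correlation; the standard errors do. The practice figures apply if Day 28 enters as a placebo score with no time term. The actual size in points is unknown because λ and the practice gain are unknown, which is the reason to commit in advance to one estimate that does not depend on λ. In an exploratory pilot this is a change that should be made, but it does not invalidate the design.

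**What to change.** 1. In section 9.1, stop naming sequence adjustment as the response to suspected carryover. Keep the regression of paired differences on sequence for period effects and other time trends.
2. Add visit (Days 28, 84, 140) as a categorical fixed effect in the PROC MIXED model.
3. Pre-specify one sensitivity analysis, always reported beside the primary: RBANS Total at Day 84, NR-first versus PBO-first, adjusted for Day 28 RBANS. Give both estimates with 95% confidence intervals.
4. State that the difference between the two estimates is not a test for carryover and does not decide which is reported. It is half the carryover estimate and just as imprecise.

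The cost is one model term and one further analysis of data already collected. The visit term raises the listed model's carryover coefficient and its SE, as shown in step 4 of the working. The sensitivity interval is wide: at ρ = 0.8 its half-width is about 3.5 points (2.03 × 1.73) against 1.8 (2.02 × 0.91) for the crossover estimate, or about 1.9 times as wide.
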